**Table 11.1 Comparative Endpoint of UKU Relative to DB Baseline**

Comparative Endpoints	Derivation Rule
Emergence of side effect Relative to DB Baseline	‘not present’ at DB Baseline and any ‘present’ in the open-label treatment period
Emergence of drug-related side effect Relative to DB Baseline	‘not present’ at DB Baseline and any drug-related ‘present’ in the open-label treatment period
Worsening of side effect Relative to DB Baseline	the most severe rating in the open-label treatment period is more severe than it was at DB Baseline
Worsening of drug-related side effect Relative to DB Baseline	the most severe drug-related rating in the open-label treatment period is more severe than it was at DB Baseline
*: the value of the open-label treatment period is defined as the worst case in the open-label treatment period.	

**Table 11.2 Comparative Endpoint of UKU Relative to the Core DB Treatment Period**

Comparative Endpoints	Derivation Rule
Emergence of side effect Relative to Core DB Treatment Period	‘not present’ in any core DB treatment period* and any ‘present’ at any open-label treatment period
Emergence of drug-related side effect Relative to Core DB	‘no drug-related present’ in any core DB treatment period* and any drug-related ‘present’ in open-label treatment period

Treatment Period	
Worsening of side effect Relative to Core DB Treatment Period	the most severe rating at any open-label treatment period is more severe than the worst case of any core DB treatment period*
Worsening of drug-related side effect Relative to Core DB Treatment Period	the most severe drug-related rating in open-label treatment period is more severe than any drug-related rating in core DB treatment period*
Note: *: is referred to any post-DB baseline visit in DB treatment period of the core study (see Table 11 of D1050301 SAP or Table 11 of D1050326 SAP).	

### ***Analysis Methods***

#### **For subjects continued from Studies D1050301 and D1050326**

For individual item and four side effect categories, numbers and percentages of subjects who experience any side effect and any drug-related side effect will be summarized by analysis subgroup at DB baseline, any core DB treatment period, and any extension treatment period (when applicable), respectively.

In addition, numbers and percentages of subjects with emergence of side effect and worsening of side effect relative to DB baseline and to the core DB treatment period will be summarized by analysis group and analysis subgroup for each individual item and each side effect category, respectively.

For each side effect category score and UKU total score, descriptive summaries (N, mean, SD, median etc.) of observed and change from DB Baseline and change from OL baseline in four UKU four category side effects scores and UKU total score will be presented by analysis group and analysis subgroup at each assessment point, W52 endpoint, and end point.

Frequency distribution of clinical global assessment of effect, patient global assessment of effect, consequence assessed by clinician will be also tabulated by visit, W52 endpoint, and endpoint and by analysis group and analysis subgroup.

#### **2.6.13. Tanner Staging and Menstrual Cyclicity**

The tanner staging is a scale of physical development in children, adolescents and adults. The scale defines physical measurements of development based on external primary and secondary sex characteristics, such as the size of the breasts, genitalia, testicular volume and development of pubic and axillary hair. Tanner staging for each measurement ranges from Stage I (Preadolescent) (numeric value 1) to Stage V (numeric value 5).

## **Analysis Methods**

All outputs for tanner staging will be tabulated separately by gender. The frequency distribution of each category of the tanner staging will be tabulated at DB baseline, OL Baseline, post-OL Baseline visit, W52 endpoint, and endpoint by analysis group. In addition, frequency distribution of changes from DB baseline and OL baseline for each category of the tanner staging will be summarized for each post-OL visit, W52 endpoint, and endpoint by analysis group. Shifts from DB baseline and OL baseline to Endpoint in tanner stage will be presented by analysis group. The frequency distribution of quality and frequency of menstrual cyclicity will be presented by analysis group.

**4. ATTACHMENTS**

**4.1. Computation of Centiles and Z-scores for Height-For-Age, Weight-For-Age (CDC only), and BMI-For-Age**

**4.1.1. WHO 2007 Reference for Growth Charts**

## COMPUTATION OF CENTILES AND Z-SCORES FOR HEIGHT-FOR-AGE, WEIGHT-FOR-AGE AND BMI-FOR-AGE

The method used to construct the 2007 WHO references relied on GAMLSS with the Box-Cox power exponential distribution (Rigby and Stasinopoulos, 2004). However, the final selected models simplified to the LMS model (Cole and Green, 1992) since none of the references required adjustment for kurtosis. As a result, the computation of percentiles and z-scores for all three indicators uses formulae based on the LMS method. However, a restriction was imposed on all indicators to enable the derivation of percentiles only within the interval corresponding to z-scores between -3 and 3. The underlying reasoning is that percentiles beyond  $\pm 3$  SD are invariant to changes in equivalent z-scores. The loss accruing to this restriction is small since the inclusion range corresponds to the 0.135th to 99.865th percentiles.

For all indicators, the tabulated fitted values of Box-Cox power, median and coefficient of variation corresponding to age (or height)  $t$  are denoted by  $L(t)$ ,  $M(t)$  and  $S(t)$ , respectively.

### *Centiles and z-scores for height-for-age*

For this indicator,  $L(t)$  is equal to 1, simplifying the Box-Cox normal distribution used in the LMS method to the normal distribution. Therefore, differences between adjacent standard deviations (e.g. between 2 SD and 3 SD) were constant for a specific age but varied at different ages.

In this case, the centiles at age  $t$  can be estimated from:

$$\begin{aligned} C_{100\alpha}(t) &= M(t)[1 + L(t)S(t)Z_\alpha]^{1/L(t)} = M(t)[1 + S(t)Z_\alpha] \\ &= M(t) + StDev(t)Z_\alpha, \quad -3 \leq Z_\alpha \leq 3 \end{aligned}$$

[figure not shown]
where  $Z_\alpha$  is the normal equivalent deviate for tail area  $\alpha$ ,  $C_{100\alpha}(t)$  is the  $100\alpha$ -th centile, and  $StDev(t)$  is the standard deviation at age  $t$  (derived from multiplying  $S(t)$  by  $M(t)$ ).

The individual z-score for a measurement  $y$  at age  $t$  was computed as:

$$Z_{ind} = \frac{\left[ \frac{y}{M(t)} \right]^{1/L(t)} - 1}{S(t)L(t)} = \frac{y - M(t)}{StDev(t)}$$

## Height-for-age BOYS

[figure not shown]
5 to 19 years (percentiles)

2007 WHO Reference

## Height-for-age GIRLS

[figure not shown]
5 to 19 years (percentiles)

2007 WHO Reference

## BMI-for-age BOYS

[figure not shown]
5 to 19 years (percentiles)

2007 WHO Reference

## BMI-for-age GIRLS

[figure not shown]
5 to 19 years (percentiles)

2007 WHO Reference

#### 4.1.2. 2000 CDC Growth Charts for the United States

Series 11, No. 246 □ Page 27

[figure not shown]
Published May 30, 2000.

SOURCE: Developed by the National Center for Health Statistics in collaboration with the National Center for Chronic Disease Prevention and Health Promotion (2000).

SAFER • HEALTHIER • PEOPLE™

Figure 9. Individual growth chart 3rd, 5th, 10th, 25th, 50th, 75th, 90th, 95th, 97th percentiles, 2 to 20 years: Boys weight-for-age

[figure not shown]

Published May 30, 2000.

SOURCE: Developed by the National Center for Health Statistics in collaboration with the National Center for Chronic Disease Prevention and Health Promotion (2000).

Figure 10. Individual growth chart 3rd, 5th, 10th, 25th, 50th, 75th, 90th, 95th, 97th percentiles, 2 to 20 years: Girls weight-for-age

[figure not shown]

Published May 30, 2000.

SOURCE: Developed by the National Center for Health Statistics in collaboration with the National Center for Chronic Disease Prevention and Health Promotion (2000).

Figure 11. Individual growth chart 3rd, 5th, 10th, 25th, 50th, 75th, 90th, 95th, 97th percentiles, 2 to 20 years: Boys stature-for-age

[figure not shown]

Published May 30, 2000.

SOURCE: Developed by the National Center for Health Statistics in collaboration with  
the National Center for Chronic Disease Prevention and Health Promotion

Figure 12. Individual growth chart 3rd, 5th, 10th, 25th, 50th, 75th, 90th, 95th, 97th percentiles, 2 to 20 years: Girls stature-for-age

[figure not shown]
Published May 30, 2000.

SOURCE: Developed by the National Center for Health Statistics in collaboration with  
the National Center for Chronic Disease Prevention and Health Promotion

SAFER • HEALTHIER • PEOPLE™

Figure 13. Individual growth chart 3rd, 5th, 10th, 25th, 50th, 75th, 90th, 95th, 97th percentiles, 2 to 20 years: Boys body mass index-for-age

Published May 30, 2000.

SOURCE: Developed by the National Center for Health Statistics in collaboration with the National Center for Chronic Disease Prevention and Health Promotion (2000).

Figure 14. Individual growth chart 3rd, 5th, 10th, 25th, 50th, 75th, 85th, 90th, 95th, 97th percentiles, 2 to 20 years: Girls body mass index-for-age

## 4.2. Cogstate Child and Adolescent Normative Data

The Cogstate normative data from healthy children and adolescents aged between 10 and 20 years are provided by Cogstate and displayed below.

### Cogstate Normative Data for Children and Adolescent Subjects

Age (years)	Detection – Speed		Identification – Speed		One Back – Speed	
	Mean	SD	Mean	SD	Mean	SD
10	2.57	0.084	2.77	0.075	2.95	0.095
11	2.54	0.081	2.74	0.074	2.92	0.089
12	2.54	0.081	2.72	0.075	2.90	0.091
13	2.52	0.078	2.70	0.071	2.88	0.088
14	2.52	0.081	2.69	0.074	2.87	0.090
15	2.51	0.078	2.68	0.071	2.86	0.089
16	2.51	0.077	2.68	0.069	2.85	0.090
17	2.50	0.075	2.67	0.066	2.84	0.090
18	2.51	0.072	2.67	0.066	2.84	0.089
19	2.50	0.066	2.67	0.060	2.83	0.085
20	2.50	0.069	2.66	0.060	2.82	0.089

Age (years)	One Card Learning – Accuracy		One Back – Accuracy	
	Mean	SD	Mean	SD
10	0.98	0.098	1.28	0.18
11	0.98	0.096	1.30	0.17
12	0.98	0.092	1.31	0.16
13	0.98	0.089	1.32	0.15
14	0.98	0.088	1.32	0.16
15	0.98	0.088	1.33	0.16
16	0.99	0.088	1.34	0.15
17	0.99	0.090	1.34	0.15
18	1.00	0.089	1.35	0.15
19	1.01	0.086	1.37	0.14
20	1.02	0.090	1.38	0.13

## 4.3. Clinical Laboratory Tests

Blood Chemistry Tests
aspartate aminotransferase
alanine aminotransferase
albumin
alkaline phosphatase
bicarbonate
blood urea nitrogen
calcium
chloride
creatinine
gamma-glutamyl transferase
phosphorous

potassium	
sodium	
total bilirubin a	
total protein	
lactate dehydrogenase	
fasting (non-random) triglycerides	
fasting (non-random) serum cholesterol	
fasting (non-random) serum high-density lipoprotein cholesterol	
fasting (non-random) serum low-density lipoprotein cholesterol	
fasting glucose	
prolactin	
whole blood hemoglobin A1c	
creatine phosphokinase	
Endocrine Tests	
free thyroxine test	
thyroid-stimulating hormone test	
Hormonal Parameters	
follicle stimulating hormone (female subjects only)	
luteinizing hormone (female subjects only)	
testosterone (male subjects only)	
estradiol (female subjects only)	
serum human chorionic gonadotropin ( $\beta$ -hCG) (female subjects $\geq$ 11 years of age only)	
urine human chorionic gonadotropin ( $\beta$ -hCG) (female subjects $\geq$ 11 years of age only)	
Hematology Tests	
white blood cell count	
white blood cell differential	
eosinophilic leukocyte count	
basophilic leukocyte count	
neutrophil count	
lymphocyte count	
monocyte count	
platelet count	
hemoglobin	
blood hematocrit	
red blood cell count	
red cell distribution width	
red blood cell indices:	
mean corpuscular volume	
mean corpuscular hemoglobin concentration	
mean corpuscular hemoglobin	
Urinalysis Tests	
color	
appearance	
total ketones	
urobilinogen	
bilirubin	
red blood cells	
leukocyte esterase	
nitrite	
pH	
protein	
specific gravity	

glucose
microscopic evaluation b
Urine Drug Screen
amphetamines
benzodiazepines
barbiturates
cocaine
tetrahydrocannabinol
ethanol
methadone
methamphetamine
opiates
phencyclidine

#### 4.4. Benzodiazepine Equivalence Table Conversion Factors to Convert Benzodiazepine Dose to Oral Equivalent Doses Standardized to Lorazepam

Benzodiazepine	Comparative dose	Benzodiazepine	Comparative dose
Alprazolam	0.5	Ketazolam	7.5
Amobarbital *	50	Loflazepate *	1.67
Barbital *	75	Lorazepam	1
Bromazepam	3	Lormetazepam *	1
Bromvalerylurea *	500	Medazepam *	10
Brotizolam *	0.5	Mexazolam *	1.67
Butoctamide *	500	Midazolam **	5 – 7.5
Chloral hydrate *	250	Nimetazepam *	5
Clobazam *	10	Nitrazepam	2.5
Clonazepam	0.25	Nordiazepam	5
Clorazepate	10	Oxazepam	15
Chlordiazepoxide	25	Oxazolam *	20
Cinolazepam **	40	Passiflora *	100
Clotiazepam *	10	Pentobarbital *	50
CloxaZolam *	1.5	Phenazepam	0.5
Delorazepam	1	Phenobarbital *	15
Diazepam	5	Prazepam	10
Estazolam	1	Quazepam	7.5
Etizolam *	1	Rilmazafone *	2
Gidazepam	50		

Fludiazepam *	0.5	Secobarbital *	50
Flunitrazepam *	1	Tandospirone *	25
Flurazepam	15	Tofisopam *	125
Flutazolam *	15	Temazepam	10
Flutoprazepam *	1.67	Triazolam	0.25
Halazepam	40	Zolpidem *	10
Haloxazolam *	5	Zopiclone *	7.5

From: Virani AS, Bezhlibnyk-Butler KZ, Jeffries JJ. *Clinical handbook of psychotropic drugs*.

18th revised version. Ashland, OH: Hogrefe & Huber Publishers; 2009.

\* *Japanese Journal of Clinical Psychopharmacology* 9: 1446, 2006.

Benzodiazepine equivalence table; V1.6 24-Feb-2012

## 4.5. Selected Adverse Events with Special Interest

### 4.5.1. Extrapyramidal Symptoms (EPS)-Related AEs

BRADYKINESIA	PARKINSONISM
DROOLING	PSYCHOMOTOR RETARDATION
DYSTONIA	TORTICOLLIS
GLABELLAR REFLEX ABNORMAL	TRISMUS
HYPOKINESIA	PSYCHOMOTOR HYPERACTIVITY
OCULOGLYRIC CRISIS	AKATHISIA
OROMANDIBULAR DYSTONIA	DYSKINESIA
EXTRAPYRAMIDAL DISORDER	TARDIVE DYSKINESIA
SALIVARY HYPERSECRETION	

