**For subjects continued from Study D1050325**

- Change in the ABC irritability subscale score and the other subscale scores (hyperactivity, stereotypy, inappropriate speech, and lethargy/social withdrawal)
- Change in the CGI-S
- Change in the CY-BOCS modified for pervasive developmental disorders (PDDs)
- Change in the CGSQ

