### **2.6.4. Adverse Events**

A treatment-emergent adverse event (TEAE) is defined as an AE onset on or after the start of open-label treatment period through 7 days after study drug discontinuation (14 days for serious adverse events and deaths). For sake of simplicity, hereafter TEAE is referred as AE in the section.

The overall incidence (ie, number and percent of subjects with one or more AE in each category) of AEs, serious AEs, deaths, AEs leading to discontinuation, drug-related AEs, serious drug-related AEs, drug-related AEs leading to discontinuation, serious AEs leading to discontinuation, and serious drug-related AEs will be summarized by analysis group and by analysis subgroup, separately.

AEs by system organ class (SOC) (number and proportion of subjects with one or more AEs within a system organ class) will be summarized by analysis group. For each AE, the percentage of subjects who experienced at least one occurrence of the given event will be provided by preferred term, grouped by system organ class, and presented by analysis group and by analysis subgroup. AEs for age subgroup summary will be also presented by SOC and preferred term and by analysis group and analysis subgroup.

Furthermore, additional summaries will be created based on the following combined preferred terms:

- Dystonia - preferred terms: dystonia, trismus, oculogyric crisis, oromandibular dystonia, tongue spasm, torticollis
- Parkinsonism - preferred terms: bradykinesia, drooling, extrapyramidal disorder, glabellar reflex abnormal, hypokinesia, parkinsonism, psychomotor retardation
- Somnolence - preferred terms: hypersomnia, sedation, somnolence, hypersomnolence

According to MedDRA coding guidelines for Lurasidone pediatric program,

- EPS-related reported terms for Tremor, Rigidity or Muscle Rigidity will be queried for further specificity. Sites will qualify if the reported term is Parkinsonian or non-Parkinsonian in nature; if confirmed, the reported term will be coded to lowest level terms of Parkinsonism; if not, the term will be coded to specific symptom.
- For reported term Restlessness, sites will qualify if the reported term is Akathisia or non-Akathisia in nature; if confirmed, the reported term will be coded to lowest level terms of Akathisia; if not, the term will be coded to specific symptom.

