In clinical database of this study, AEs with preferred term of Tremor, Muscle Rigidity, and Cogwheel Rigidity should be read as non-Parkinsonian; AEs with preferred term of Restlessness should be read as non-Akathisia. Due to above reasons, preferred terms Tremor, Muscle Rigidity, and Cogwheel Rigidity are not included in the list for combined preferred terms of 'Parkinsonism'. In addition, these three preferred terms plus term Restlessness are not included in the list for extra-pyramidal symptoms (EPS)-related AEs in [Attachment 4.5.1](#).

Summaries of AEs by preferred term only by analysis group for both combined and uncombined terms will be generated as well, respectively.

In addition, the incidence of AEs (by preferred term, grouped by SOC, and presented by analysis group and by analysis subgroup) will also be summarized by severity, by the relationship to study medication, by the action taken regarding the study medication, as well as by the outcome. The relationship to study medication will be presented by 2 categories: related (which includes possibly related, probably related, and related, as determined by investigators), and not related (which includes unrelated and unlikely to be related, as determined by investigators). Listings will also be generated for deaths, SAEs, and discontinuations due to AEs. All adverse events regardless of treatment emergent status will be provided in the AE data listing.

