### 4.5.2. Metabolic-Related AEs

BLOOD CHOLESTEROL INCREASED	HYPERCHOLESTEROLAEMIA
BLOOD GLUCOSE INCREASED	HYPERGLYCAEMIA
BLOOD INSULIN INCREASED	HYPERINSULINAEMIA
BLOOD TRIGLYCERIDES INCREASED	HYPERLIPIDAEMIA
DIABETES MELLITUS	HYPERTRIGLYCERIDAEMIA
DYSLIPIDAEMIA	IMPAIRED FASTING GLUCOSE
GLUCOSE TOLERANCE IMPAIRED	LOW DENSITY LIPOPROTEIN INCREASED
GLYCOSURIA	METABOLIC SYNDROME
GLUCOSE URINE PRESENT	TYPE 2 DIABETES MELLITUS

GLYCOSYLATED HAEMOGLOBIN INCREASED	TYPE 1 DIABETES MELLITUS
HIGH DENSITY LIPOPROTEIN DECREASED	WEIGHT INCREASED
WEIGHT DECREASED	LOW BLOOD SUGAR

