#### 4.5.5. Hyperactivity Related AEs

High-level Term		
Increased Physical Activity Levels	Increased Physical Activity Levels	Attention Deficit and Disruptive Behavior Disorders
Preferred Term		
Psychomotor Hyperactivity	Restlessness	Attention Deficit/Hyperactivity Disorder
Lower Level Term		
Activity motor exaggerated	Activity motor exaggerated	Marked restlessness
Behavior hyperactive	ADHD, combined type	Muscular unrest
Behaviour hyperactive	ADHD, predominantly hyperactive-impulsive type	Physically restless
Hyper	Attention deficit disorder of childhood with hyperactivity	Psychomotor restlessness
Hyperactive	Hyperactive child syndrome	Restless
Hyperactivity	Hyperactivity syndrome aggravated	Restlessness
Increased activity	Hyperkinesis of childhood with developmental delay	Restlessness (drug related)
Irritable hyperkinesis	Hyperkinetic conduct disorder of childhood	Restlessness aggravated
Motor activity exaggerated	Hyperkinetic syndrome	Restlessness marked
Muscular hyperactivity	Hyperkinetic syndrome of childhood	Unrest
Overactive	Other specified manifestations of hyperkinetic syndrome of childhood	
Overactivity	Overactive child	
Pedaling	Syndrome hyperkinetic	
Psychomotor agitation	Unspecified hyperkinetic syndrome of childhood	
Psychomotor excitability		
Psychomotor hyperactivity		

Source: Lurasidone IND 61292 SN0434, Communicated with FDA on 10/24/2014

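### Two special-interest AE composites mix unlike events: EPS includes psychomotor hyperactivity, and metabolic AEs pool weight loss and low blood sugar with weight gain and hyperglycaemia

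*SAP*

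**What the plan says.** SAP 2.6.4 (AEs with Special Interest) combines the preferred terms in Attachments 4.5.1 to 4.5.4 into four groups. It reports incidence and an exposure-adjusted incidence rate for each, by analysis group and subgroup. The EPS group is also shown split into akathisia and non-akathisia events.

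**EPS.** Attachment 4.5.1 has 17 preferred terms, one of which is "PSYCHOMOTOR HYPERACTIVITY". Attachment 4.5.5 lists "Psychomotor Hyperactivity" as a hyperactivity term, with lower level terms such as "Behaviour hyperactive". The SAP uses that attachment to summarise hyperactivity events that begin after the last dose.

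SAP 2.6.4 also sets a coding rule for some motor terms. Sites are asked whether reported restlessness is akathisia. If it is, it is coded to akathisia; if not, it stays as Restlessness. For tremor and rigidity, "EPS-related reported terms for Tremor, Rigidity or Muscle Rigidity will be queried for further specificity". The terms left after these queries are kept out of the EPS list: "these three preferred terms plus term Restlessness are not included in the list for extra-pyramidal symptoms (EPS)-related AEs".

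**Metabolic.** Attachment 4.5.2 has 24 terms. It includes weight increase, hyperglycaemia, diabetes and lipid terms, together with "WEIGHT DECREASED" and "LOW BLOOD SUGAR". No split by direction is planned.

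**The concern.** A composite is useful when its terms describe one kind of harm. These two do not quite do so.

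For EPS, hyperactivity is part of the illness in two of the three populations. In D1050325 the ABC hyperactivity subscale is an effectiveness endpoint (SAP 2.3.1.1). In D1050326 the ADHD-RS has a hyperactivity/impulsivity subscale (SAP 2.3.1.1.8), and the YMRS scores raised motor activity and energy (SAP 2.6.8). Protocol 13.1 counts worsening of an existing condition as an AE. A flare of illness can therefore be recorded as psychomotor hyperactivity and then be counted as a motor side effect.

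For the metabolic group, a subject whose only event is weight loss adds as much to the rate as one with new diabetes. A rise in the rate then does not tell the reader which way weight or glucose moved.

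Long-term safety is part of the primary objective and the study has no control arm. Readers will take the absolute rates at face value, with no comparator to show that a group is mixed.

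**Working it through.** The plan states no numerical figure on this point, so the check is a comparison of lists, followed by an illustration under assumed rates.

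**1. EPS list against hyperactivity list.** Of the 17 EPS preferred terms and the 3 hyperactivity preferred terms (psychomotor hyperactivity, restlessness, ADHD), one appears on both: psychomotor hyperactivity. I rely only on the first lower-level-term column of Attachment 4.5.5. The other two columns look displaced in the extracted text.

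**2. Treatment of two similar terms.**

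| | Restlessness | Psychomotor hyperactivity |
|---|---|---|
| Site query described? | Yes, akathisia or not | No |
| On the hyperactivity list? | Yes | Yes |
| Counted as EPS? | Only if coded to akathisia | Always |

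**3. Double use.** A treatment-emergent event may begin up to 7 days after discontinuation (14 if serious). One psychomotor hyperactivity event in that window could appear as EPS in one table and as post-dose hyperactivity in another.

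**4. Effect on the EPS rate.** Let *a* be the EPS incidence without the term, and *h* the incidence of psychomotor hyperactivity among subjects with no other EPS term. Then

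composite = *a* + (1 − *a*) × *h*.

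Both *a* and *h* are assumptions. Each cell shows the composite and its ratio to *a*.

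| *a* | *h* = 1% | *h* = 2% | *h* = 5% |
|---|---|---|---|
| 5% | 5.95% (1.19) | 6.90% (1.38) | 9.75% (1.95) |
| 10% | 10.90% (1.09) | 11.80% (1.18) | 14.50% (1.45) |
| 15% | 15.85% (1.06) | 16.70% (1.11) | 19.25% (1.28) |

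For D1050326 (n = 306) with *a* = 10% and *h* = 2%, this is 306 × 0.118 = 36.1 against 306 × 0.10 = 30.6 subjects. For D1050325 (n = 125) it is 125 × 0.118 = 14.8 against 12.5.

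**5. The akathisia split does not help.** Psychomotor hyperactivity falls in the non-akathisia row. Subjects it adds to the EPS total have no other EPS term. Subjects it adds to the non-akathisia row include all of those, plus any whose only other EPS term is akathisia. The row therefore gains at least as many subjects as the total, on a base that is no larger.

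**6. Preferred-term tables bound the answer but do not give it.** If the composite incidence is *c* and the term's own incidence is *p*, the incidence without the term lies between *c* − *p* and *c*. Where it lies depends on how many subjects also had another EPS term, which only subject-level data show. The exposure-adjusted rate cannot be rebuilt from those tables either.

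**7. Metabolic list.** Of the 24 terms, 22 point to weight gain, raised glucose or insulin, diabetes, metabolic syndrome or adverse lipids. Two, weight decrease and low blood sugar, point the other way (22 + 2 = 24). The documents give no rates from which to size the effect.

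**The case against.** The strongest reply is that these lists are pre-specified, and their terms are to be medically reviewed and fixed before lock. A term may sit on two lists that serve two purposes without contradiction. Any inflation of EPS overstates a harm rather than hiding one, and no hypothesis is tested. Stable baseline hyperactivity is not an AE, since an AE must be new or a worsening. EPS is also measured directly by BARS, AIMS and SAS. The metabolic heading is neutral as to direction. Glucose, insulin, HOMA-IR, lipids, weight, BMI and weight-status shifts are analysed separately (SAP 2.6.5 and 2.6.7). Preferred-term tables show each component.

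Most of this stands and keeps the point small. It does not make the two composites interpretable on their own. The medical review is a route for correction; the documents do not show that it settled this overlap.

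A reader might also infer that cogwheel rigidity is wrongly left out and should be added to Parkinsonism and EPS, because the query rule does not name it. The documents do not support that. The rule covers reported rigidity, which can include a cogwheel report. Events confirmed as parkinsonian are coded to Parkinsonism, which is in both groups. SAP 2.6.4 says that events left under Cogwheel Rigidity are to be taken as non-parkinsonian, so adding the term would count events that the plan has ruled out. At most, the sponsor could confirm that cogwheel reports went through the query.

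**Conclusion.** The point holds as a minor one. The EPS composite includes one term that the SAP itself classes as hyperactivity and does not query, and the metabolic composite mixes opposite directions. The 1.06 to 1.95 range for EPS is illustrative only: it rests on assumed rates of 5–15% and 1–5%, and the real effect could be negligible if the term is rare or mostly occurs alongside other EPS terms. The metabolic effect cannot be sized at all.

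It would go too far to say that the lists misstate metabolic harm, or that metabolic safety cannot be judged in this study. The heading claims no direction, and the laboratory and weight analyses supply it. What is lost is the meaning of two composite incidences and their exposure-adjusted rates, which the other planned tables do not restore.

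**What to change.** Keep Attachments 4.5.1 and 4.5.2 as they are, and add supplementary rows before final database lock 2 (targeted for November 21, 2018 in SAP Section 1), each with incidence and exposure-adjusted rate:

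- EPS total, and EPS non-akathisia, without psychomotor hyperactivity.
- Metabolic AEs in two rows: the 22 terms for weight gain, hyperglycaemia/diabetes and dyslipidaemia, and separately weight decrease with low blood sugar.

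The cost is a few table rows and no new data. Lock 1 occurred on June 15, 2018 and the schizophrenia report is complete, so rows for the 271 of 702 subjects from D1050301 should be labelled as supplementary and added after lock 1. Leaving the lists unchanged keeps the pre-specified rates consistent with that report.
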